#### **8.11.5 Precautions**

Adverse events should be treated in accordance with standard medical practice. During the course of the study, the overall safety, and tolerability of all study treatments will be reviewed by the sponsor and the investigator.

#### **8.11.6 Reporting of Adverse Events Associated with Study Drug Overdose, Misuse, Abuse or Medication Error**

AEs associated with study drug overdose, misuse, abuse, and medication error refer to AEs associated with uses of the study drug outside of that specified by the protocol. Overdose, misuse, abuse, and medication error are defined as follows:

Overdose: Accidental or intentional use of the study drug in an amount higher than the protocol-defined dose

Misuse: Intentional and inappropriate use of study drug not in accordance with the protocol

Abuse: Sporadic or persistent intentional excessive use of study drug accompanied by harmful physical or psychological effects

Medication error: Any unintentional event that causes or leads to inappropriate study drug use or subject harm while the study drug is in the control of site personnel or the subject.

All AEs associated with overdose, misuse, abuse, or medication error should be captured on the Adverse Event eCRF and also reported using the procedures detailed in Reporting of SAEs even if the AEs do not meet serious criteria. Abuse is always to be captured as an AE. If the AE associated with an overdose, misuse, abuse, or medication error does not meet serious criteria, it must still be reported using the SAE form and in an expedited manner but should be noted as non-serious on the SAE form and the Adverse Event eCRF.

### **8.12 Concomitant Medications and Concomitant Therapies**

Any medication (including OTC medications) taken by a subject within 30 days prior to the Screening Visit and during the course of the study and the reason for use of the medication will be recorded on the eCRF. Upon entering the study, each subject will be instructed to report the use of any medication (including OTC medications) to the investigator.

### **8.13 Prohibited Medications**

The following medications are prohibited with the appropriate washout period, if any, for each prohibited medication:

- Retroviral/antiretroviral medications, except for remdesivir
- Any experimental drug/clinical trial, except for remdesivir and convalescent plasma
- colchicine

### **8.14 Pharmacokinetic Sampling and Handling**

The limited sampling schedule is used due to limitations on study personnel entering the patient's room during the day.

The blood sample should be collected in a 6 mL K2EDTA blood collection tube at each collection time.

Immediately after collection, the tube will be gently inverted several times to mix the anticoagulant with the blood sample. The blood sample should be kept at room temperature until processed. The blood samples should be processed within 60 minutes after collection. The plasma fraction will be separated by placing the collection tube into a centrifuge for 10 minutes at 1,500 x g (at room temperature). The plasma fraction will be withdrawn by pipette and divided into two polypropylene freezing tubes (with each tube receiving approximately equal aliquots). All plasma samples will be placed into a freezer at -20°C (or below) within 90 minutes after collection. (NOTE: A flash freezing in dry ice or liquid nitrogen is NOT required under this protocol but may be used.)

## 8.15 Plasma Sample Labels for Pharmacokinetic Samples

The plasma freezing tube labels will contain the following information:

- Subject Number
- Study Number
- Site Number
- Prior Dosing time (hour and minute)
- Sample time (hour and minute)
- Aliquot Number: Aliquot A or B
- Species and Matrix: Human Plasma
- Sample Sequence Number
- Barcode Number

Labels will be fixed to freezing tubes in a manner that will prevent the label from becoming detached after freezing.

All plasma samples will be stored frozen (-20°C or below). Details of the method validation and sample analysis will be included with the final report.

## 9.0 STATISTICAL ANALYSIS

### 9.1 Sample Size Calculation

In the Phase 2, the VERU-111 treated group showed a 5.3% mortality rate compared to a 30% mortality rate in the Placebo group in the same patient population.

Approximately, 210 subjects are planned to be randomized at a 2:1 ratio into two treatment arms (140 subjects in the VERU-111 treated group and 70 subjects in the Placebo treated group). Randomization will be stratified by baseline WHO Ordinal Scale score of 4, 5 and 6 such that subjects with a WHO Ordinal Scale of 4, 5 and 6 at baseline will be approximately equally distributed between the treatment groups. Assuming a rate of mortality of 5% in the VERU-111 treated group and 25% in the Placebo treated group, the above sample sizes will yield 95% confidence interval of [-0.308, -0.092] for the risk difference between treatment groups. Other scenarios are shown in the table below.

$$\text{Confidence interval} = (p_1 - p_2) \pm z^* \sqrt{(p_1(1-p_1)/n_1 + p_2(1-p_2)/n_2)}$$

where:

- $p_1, p_2$ : sample 1 proportion, sample 2 proportion
- $z$ : the z-critical value based on the confidence level
- $n_1, n_2$ : sample 1 size, sample 2 size

Table of Alternative 95% Confidence intervals for the difference between Treatment Groups:  
 Mortality at Day 60

VERU-111	Placebo	Difference	LOWER 95% CI	UPPER 95% CI
0.05	0.15	-0.1	-0.191107629	-0.008892371
0.05	0.2	-0.15	-0.250420118	-0.049579882
0.05	0.25	-0.2	-0.307672652	-0.092327348
0.05	0.3	-0.25	-0.363261644	-0.136738356
0.1	0.15	-0.05	-0.147297482	0.047297482
0.1	0.2	-0.1	-0.206067903	0.006067903
0.1	0.25	-0.15	-0.262958399	-0.037041601
0.1	0.3	-0.2	-0.318297929	-0.081702071
0.15	0.15	0	-0.102449012	0.102449012
0.15	0.2	-0.05	-0.160812454	0.060812454
0.15	0.25	-0.1	-0.21742487	0.01742487
0.15	0.3	-0.15	-0.27256998	-0.02743002

With significance level  $\alpha=0.05$ , and a 2:1 ratio of enrollment into the VERU-111 and Placebo arms respectively, the sample size is adequate to achieve  $>92\%$  power assuming the treatment estimates stated above.

NOTE: The IDMC will monitor efficacy and safety and may make a recommendation to stop the study based on treatment success according to the statistical analysis plan and IDMC charter for this study.

## 9.2 Analysis Sets

**Intent-to-Treat (ITT) population:** All randomized subjects will be included in this population.

**Modified Intent-to-Treat (mITT) analysis set:** All randomized subjects who do not have any major protocol violations will be included in the mITT population.

**Safety (SAF) analysis set:** All randomized subjects who received at least one dose of study medication (VERU-111 or Placebo) will be included in this population. The SAF population will be used as the safety population.

## 9.3 Analysis Scope

The Intent-to-Treat (ITT) analysis scope will include all data collected from randomization to the end of the study at Day 60. This will be considered the primary analysis scope for the primary analysis.

## 9.4 Efficacy Analyses

A statistical analysis plan will be written for this Phase 3 clinical study. A detailed description of the analyses that will be conducted will be included in that document.

### 9.4.1 Primary Endpoint

The primary endpoint for the study will be the proportion of subjects that die on study (up to Day 60).

The number and percentage of deaths will be summarized by treatment group. Mortality rates will be analyzed using a logistic regression model. This model will include treatment as a factor and study site, gender, remdesivir use (No/Yes), dexamethasone use (No/Yes) and WHO Ordinal Scale for Clinical Improvement at baseline as a covariates. The model will be fitted using logit link function. Odds ratios, standard errors, 95% confidence intervals and p-values for the treatment difference will be presented.

The primary analysis will be performed on the ITT analysis set and the ITT data scope regardless of patient's use of rescue medications, protocol violations or investigational product discontinuation consistent with the treatment policy strategy. Every effort will be made to collect vital status up to the end of the study period. Missing data for subjects who are lost to follow up will be imputed using multiple imputation methods. Details for the imputation will be given in the Statistical Analysis Plan (SAP).

### 9.4.2 Secondary Analyses of the Primary Endpoint

The primary endpoint, mortality rate, will also be assessed in the subset of mITT patients.

To obtain risk differences between treatment groups, the same analysis as described above will be fitted except identity link function will be used.

Additionally, mortality rates will be summarized using Kaplan-Meier (KM) survival curves and equality of treatment groups will be tested using log-rank test. Hazard ratios will be calculated using the Cox proportional hazards model including terms for treatment, study site, gender, remdesivir use (No/Yes), dexamethasone use (No/Yes) and WHO Ordinal Scale for Clinical Improvement at baseline. Any subjects that are lost to follow-up or terminated early prior to death will be censored at the day of their last observed assessment or last captured event.

#### 9.4.2.1 Sensitivity Analyses

A sensitivity analysis using the tipping-point approach will be conducted to assess the robustness of the primary analysis approach.

Missing endpoints will be re-assigned in a series of analyses that are progressively more in favor of placebo.

The tipping point analysis will consider the full range of possible response rates in the subjects with missing data in the primary analysis. This will be done by systematically changing assumed response rates from 0% to 100% in a stepwise manner. The imputation will be performed independently within the two treatment groups so that, in the most extreme case, the imputed response rate in the VERU-111 arm will be 0% and 100% in the placebo arm.

Multiple imputation will be used for each pair of response rates under consideration. Both the imputation model and the analysis model will incorporate the covariates as used in the primary analysis.

Details for the imputation will be given in the SAP.

## 9.5 Secondary Endpoint

Primary analysis of secondary endpoints will be performed on the ITT analysis set and the ITT data scope regardless of patient's use of rescue medications, protocol violations or investigational product discontinuation consistent with the treatment policy strategy.

Full details for the handling of missing data, and consideration of subjects that die during the study for those endpoints that do not directly incorporate death, will be included in the Statistical Analysis Plan.

### 9.5.1 Proportion of patients alive and free of respiratory failure at Day 29, Day 15 and Day 22

Respiratory failure is defined as endotracheal intubation and mechanical ventilation, extracorporeal membrane oxygenation, high-flow nasal cannula oxygen delivery, noninvasive positive pressure ventilation, clinical diagnosis of respiratory failure with initiation of none of these measures only when clinical decision making is driven solely by resource limitation.

This analysis will compare the percentage of subjects that are alive without respiratory failure (responder) on Day 29 and on Day 15 and on Day 22.

Proportion of subjects alive and free of respiratory failure will be analyzed separately at each timepoint using the same logistic regression methodology as primary endpoint ([section 9.4.1](#)).

#### 9.5.1.1 Days in ICU

Days in ICU will be summarized using descriptive statistics (n, mean, standard deviation, median, minimum, and maximum) by treatment group.

For subject who die, days in ICU will be set to the worst possible outcome (29 days) to give deaths unfavorable value in the analysis.

Treatment comparison will be based on analysis of covariance (ANCOVA) model including treatment as a factor and study site, gender, remdesivir use (No/Yes), dexamethasone use

(No/Yes) and WHO Ordinal Scale for Clinical Improvement at baseline as covariates. Treatment difference, standard error, 95% confidence interval and p-value will be presented.

#### **9.5.1.2 Change from baseline in WHO Ordinal Scale for Clinical Improvement at Day 15, Day 22 and Day 29**

Baseline for WHO Ordinal Scale for Clinical Improvement will be the last available record prior to first dose of study medication.

For subject who die, WHO Ordinal Scale for Clinical Improvement will be set to the worst possible outcome (8 – death) for the following planned timepoints to give deaths unfavorable value in the analysis. For subjects who are discharged early, or are otherwise having missing values, following timepoints use data from multiple imputation. Details for the imputation will be given in the SAP.

WHO Ordinal Scale for Clinical Improvement will be summarized using frequencies and percentages by treatment group and timepoint. Also change from baseline will be summarized.

Change from baseline will be analyzed as ordinal response using proportional odds logistic regression. Analysis will be performed separately for each timepoint (Day 15, Day 22, Day 29). Proportionality of odds will be tested and if the proportionality assumption does not hold, then non-proportional odds model will be fitted. Model will include treatment as fixed effect and study site, gender, remdesivir use (No/Yes), dexamethasone use (No/Yes) and WHO Ordinal Scale for Clinical Improvement at baseline as covariate. Odds ratio, 95% confidence interval and p-value for the treatment difference will be presented. Distribution of change from baseline will be plotted in stacked bar plot by treatment group and time point.

Proportional (or non-proportional) odds model will be performed only using the imputed data to include all subjects in the analysis.

Additionally, descriptive statistics (n, mean, standard deviation, median, minimum and maximum) will be summarized for absolute values and change from baseline by treatment group and visit.

Additionally, change from baseline will be analyzed using mixed model for repeated measures (MMRM) including treatment, visit and treatment-by-visit interaction as fixed effects and study site, gender, remdesivir use (No/Yes), dexamethasone use (No/Yes) and WHO Ordinal Scale for Clinical Improvement at baseline as covariate. The resulting F-tests will be based on Kenward-Roger's adjusted degrees of freedom. Least squares means, standard errors, 95% confidence intervals and p-values for treatments and treatment differences at each visit will be presented.

MMRM analysis will be performed only using the imputed data to include all subjects in the analysis.

#### **9.5.1.3 Days on mechanical ventilation**

Days on mechanical ventilation will be summarized using descriptive statistics (n, mean, standard deviation, median, minimum and maximum) by treatment group.

For subject who die, days on mechanical ventilation will be set to the worst possible outcome (29 days) to give deaths unfavorable value in the analysis.

Days on mechanical ventilation will be analyzed using the same methodology as for Days in ICU ([section 9.5.1.2](#)).

#### **9.5.1.4 Days in hospital**

Days in hospital will be summarized using descriptive statistics (n, mean, standard deviation, median, minimum and maximum) by treatment group.

For subject who die, days in hospital will be set to the worst possible outcome (29 days) to give deaths unfavorable value in the analysis.

Days in hospital will be analyzed using the same methodology as for Days in ICU ([section 9.5.1.2](#)).

#### **9.5.1.5 Mean change from baseline in Viral load to Day 9**

The mean change in viral load from baseline to Day 9 will be assessed.

Descriptive statistics (n, mean, standard deviation, median, minimum and maximum) will be summarized for absolute values, and change from baseline by treatment group.

Change from baseline will be analyzed using the same methodology as for change from baseline in WHO score ([section 9.5.1.3](#)).

### **9.6 Pharmacokinetic Analysis**

The pharmacokinetic samples for assessment of VERU-111 levels will be taken at baseline (prior to dosing on Day 1) and then prior to dosing on Days 3 and 9.

An evaluation of baseline levels versus effectiveness of VERU-111 will be conducted.

Pharmacokinetic concentration data will be summarized using descriptive statistics (n, mean, standard deviation, median, minimum and maximum). CV%, geometric mean, geometric SD and geometric CV% will be presented.

All PK data will be listed.

### **9.7 Safety Analysis**

The frequency of adverse events (AEs) will be tabulated by MedDRA term and system organ class. The incidence of AEs and the maximum intensity and frequency of AEs will be

summarized. A new onset AE is defined as an AE that was not present prior to treatment with study medication but appeared following treatment or was present at treatment initiation but worsened during treatment. An AE that was present at treatment initiation but resolved and then reappeared while the subject was on treatment is a new-onset AE (regardless of the intensity of the AE when the treatment was initiated).

All laboratory results, vital sign measurements, and other safety variables will be summarized using appropriate descriptive statistics. Changes from baseline will be computed and will be summarized using appropriate descriptive statistics.

A summary of the number of subjects developing treatment emergent values of ALT and AST  $\geq 3x$  ULN,  $5x$  ULN, and  $10x$  ULN, respectively and a shift table for individual subjects shifts from baseline to maximum observed value by category:  $<3x$  ULN,  $\geq 3x$  ULN,  $\geq 5x$  ULN and  $\geq 10x$  ULN will be provided. Additionally, a summary of patients that develop Drug Induced Liver Injury by Hy's Law will be provided.

Safety data will be summarized utilizing the SAF analysis set.

### **9.7.1 Independent Data Monitoring Committee (IDMC)**

An Independent Data Monitoring Committee (IDMC) will review the unblinded safety data from this Phase 3 study, including all SAEs, approximately every 4 weeks. The efficacy data will be reviewed at the specified timepoint for the interim efficacy analysis when approximately 50% of the subjects have completed Day 60.

The recruitment of this Phase 3 study is expected to be completed within 9 months of first patient, first dose.

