### **9.7.2 Interim Analysis**

An efficacy interim analysis of the primary endpoint, all-cause mortality at Day 60, will be conducted when approximately 71.4% of the subjects (~150 subjects) have completed Day 60, died or withdrawn for other reasons. The first 150 patients randomized into the study will be included in the planned interim analysis. The interim and final analyses will follow an O'Brien-Fleming group sequential design, with a plan of stopping the trial at the interim analysis if the results are statistically significant in favor of VERU-111. The criterion for efficacy at the interim analysis will be a two-sided 0.0160 p-value (a one-sided p-value  $\leq 0.0080$  in favor of VERU-111). If the criterion is not met, the trial will continue, and the final analysis will have a criterion for efficacy of a two-sided p-value  $\leq 0.0452$  (one-sided 0.0226 in favor of VERU-111).

In addition, an estimate of the conditional power that the trial will be positive (statistically significant difference for final analysis) will be provided to the IDMC at regular intervals. If the conditional power is below 0.30 this may suggest termination for futility. However, this would not be a binding rule. Factors other than the conditional power will be considered by the IDMC when weighing the futility of the study as a whole after carefully evaluating various factors, including among others, enrolment rate and safety.

[figure not shown]
The interim analyses will be conducted by an independent statistician and provided to the IDMC. The sponsor will not be unblinded to the data and will only be notified of the recommendation of the IDMC to stop or continue the trial for futility. The sponsor will make such a decision after carefully evaluating various factors, including among others, enrolment rate and safety.

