7 INTERIM ANALYSIS

Interim analyses are described in separate IDMC SAP.

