8 INDEPENDENT DATA MONITORING COMMITTEE (IDMC) ANALYSIS

Independent Data Monitoring Committee (IDMC) analyses and interim analyses are described in separate IDMC analysis plan.

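### Protocol 9.7.1 times the single efficacy interim at about 50% of subjects, 9.7.2 at about 71.4%; the stated stopping criteria fit only the second

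*Protocol*

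**What the plan says.** Protocol 9.7.1, on the IDMC, has safety reviewed about every four weeks and efficacy reviewed once, at the "interim efficacy analysis when approximately 50% of the subjects have completed Day 60". With 210 planned subjects (Protocol 6.1 and 9.1, SAP section 4), that is 105 subjects.

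Protocol 9.7.2, the next section, says that the efficacy interim "will be conducted when approximately 71.4% of the subjects (~150 subjects) have completed Day 60, died or withdrawn for other reasons". It then fixes the cohort: "The first 150 patients randomized into the study will be included in the planned interim analysis". On the boundary it says: "The interim and final analyses will follow an O'Brien-Fleming group sequential design". It adds: "The criterion for efficacy at the interim analysis will be a two-sided 0.0160 p-value" (one-sided 0.0080 in favor of VERU-111). The final criterion is a two-sided 0.0452 (one-sided 0.0226). The trial stops at the interim only for a result in favor of VERU-111.

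Other places give no timing. Protocol 9.1 says that the IDMC "may make a recommendation to stop the study based on treatment success according to the statistical analysis plan and IDMC charter for this study". SAP section 7 says "Interim analyses are described in separate IDMC SAP", and SAP section 8 likewise says that IDMC "analyses and interim analyses are described in separate IDMC analysis plan". That plan is not among the documents supplied.

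**The concern.** A group sequential criterion belongs to a particular look time. The earlier the look, the stricter an O'Brien-Fleming-type interim criterion has to be. Here the section on the committee's remit and the section on the interim analysis give different times for one look, and no rule says which section governs. Someone who drew up the IDMC schedule from 9.7.1 and took the criterion from 9.7.2 would test mortality at 50% against a threshold built for 71.4%. The trial could then stop for efficacy earlier, and on weaker evidence, than the boundary allows. Even without that, two look times for the primary endpoint leave any early stop open to challenge.

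**Working it through.** **Inputs.** N = 210, 2:1 (Protocol 9.1). Look times: 50% (9.7.1) and 150 subjects (9.7.2). Criteria: one-sided 0.0080 and 0.0226 (9.7.2). Overall level: two-sided 5% (SAP 6.11), taken as 2.5% in each direction. Planned mortality: 5% on VERU-111 and 25% on placebo (Protocol 9.1).

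**1. Look times as information fractions.** 150/210 = 0.714, which agrees with the 71.4% in 9.7.2. 0.50 × 210 = 105.

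**2. Reproduce the plan's criteria.** Lan-DeMets O'Brien-Fleming-type spending at one-sided 0.025 is α(t) = 2[1 − Φ(z/√t)], with z = 2.2414, the upper 0.0125 point. At t = 0.7143, z/√t = 2.652 and α(t) = 0.0080, or two-sided 0.0160. The final criterion is solved from the joint normal distribution of the two test statistics (correlation √t) so that the total one-sided error is 0.025. This gives two-sided 0.0452. Both match 9.7.2 to four decimals.

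**3. The same calculation at 50%.** At t = 0.50, z/√t = 3.170 and α(t) = 0.00153, or two-sided 0.0031. The final criterion becomes 0.0490.

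| Two-sided criteria, interim / final | t = 0.50 | t = 150/210 |
|---|---|---|
| Lan-DeMets O'Brien-Fleming type | 0.0031 / 0.0490 | 0.0160 / 0.0452 |
| Classical O'Brien-Fleming | 0.0052 / 0.0480 | 0.0174 / 0.0444 |
| Stated in 9.7.2 | – | 0.0160 / 0.0452 |

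At 50%, an interim criterion of 0.0160 is about five times the Lan-DeMets value and about three times the classical one. The final 0.0452 taken alone would be slightly stricter than needed.

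**4. Error if the stated criteria were used at 50%.** The interim stops only in favor of VERU-111 (z above 2.409, one-sided 0.0080). The final test uses one-sided 0.0226 (z = 2.003). With no treatment effect and t = 0.50:

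- False claim for VERU-111, at either look: 2.69%, against 2.50%. The excess is 0.19 percentage points.
- False stop at the interim itself: 0.80%, against 0.15% under the matching spending function.
- Rejection against VERU-111, possible only at the final analysis: 2.26%.
- Both directions together: 2.69% + 2.26% = 4.95%.

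**5. Could the two timings be the same moment?** Section 9.7.1 counts Day 60 completers; 9.7.2 also counts deaths and withdrawals. For 150 resolved subjects to contain only 105 completers, 45 of 150 (30%) would have to have died or withdrawn. Planned pooled mortality is (140 × 0.05 + 70 × 0.25)/210 = 24.5/210 = 11.7%. That leaves about 132 completers among 150, or 63% of 210, before withdrawals. The difference in counting rule narrows the gap but does not close it at the planning assumptions.

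**The case against.** The strongest reply is that 9.7.2 is the operative section. It gives the count, the cohort, the counting rule and both criteria, whereas 9.7.1 only describes the committee and defines no boundary. Anyone who follows 9.7.2 runs the look on 150 of 210 with a correct boundary, and using 0.0160 on 105 subjects would breach its cohort sentence. This stands, and it is why the harm is conditional. It does not remove the contradiction.

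The separate IDMC plan or charter may already give a single timing, and a figure in 9.7.2 is missing from the text supplied. Both are possible. A correct IDMC plan would still disagree with 9.7.1 as written.

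A reader might infer that the overall error exceeds 5%, because doubling 2.69% gives 5.38%. The documents do not support that. Doubling counts an interim rejection against VERU-111 as a claim, and 9.7.2 provides no such stop.

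A reader might also infer that the boundary is wrong because the classical O'Brien-Fleming values differ from the stated ones. The Lan-DeMets form reproduces them, and 9.7.2 does not say which form it uses. The missing name is a matter of detail, and the IDMC plan may supply it.

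The conditional power reports to the IDMC concern non-binding futility and add no second efficacy look.

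**Conclusion.** The inconsistency is real: one efficacy look has two stated timings in current protocol text, and the supplied documents do not resolve it. The criteria identify 150/210 as the timing they were built for, so the 50% in 9.7.1 is the figure out of place. The boundary in 9.7.2 is sound at its own timing.

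The consequence is small and depends on a combination that no section prescribes, namely the 9.7.1 timing with the 9.7.2 criteria. In that case the one-sided error in favor of VERU-111 is 2.69% against 2.50%, and the total over both directions, about 4.95%, stays below 5%. These figures assume that information is proportional to resolved subjects, with 105 of 210 resolved at the look; more resolved subjects would bring the one-sided error closer to 2.50%.

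The SAP amendment table records a change of sample size from 300 to 210, and 150/300 = 50%. A reader might infer that the 50% was carried over. The documents do not say so, and the conclusion does not rest on it. The point should be fixed, as a correction of wording.

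**What to change.** In Protocol 9.7.1, replace the 50% clause with the trigger used in 9.7.2: about 71.4% of subjects, being the first 150 randomized, each having completed Day 60, died or withdrawn for another reason. Check that the separate IDMC plan and the charter give the same timing.

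Optionally, confirm and name in 9.7.2 the spending function actually used, so that both criteria can be recomputed if the look falls at another information fraction.

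The cost is one clause, plus one sentence if the option is taken. Sample size, data collection and the stated criteria do not change.
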